Appendix F: Post-operative assessments [40](#)

Appendix G: Post-operative day 1 assessment [42](#)

Deleted: 39

Deleted: 41

PROJECT SUMMARY

Justification.

Over 900,000 abortion procedures are performed annually in the United States [1]. For many women, pain relief during abortion is inadequate despite the use of non-steroidal anti-inflammatory drugs, local anesthetics, opioids, and/or moderate sedation. Research on pain control during abortion has focused on methods for relief during first-trimester suction curettage with little research dedicated to pain during dilation and evacuation (D&E). Gabapentin (Neurontin®) has emerged as an effective adjunct to pain management for a variety of surgical procedures. Gabapentin is inexpensive and is also effective in reducing anxiety, nausea, and vomiting. The addition of pre-operative gabapentin to moderate sedation during D&E may lead to increased patient satisfaction and pain relief without significantly increasing risk or cost.

Proposed Research.

We propose a randomized controlled double-blinded trial evaluating the use of adjunct gabapentin versus placebo in addition to moderate sedation during D&E. We hypothesize that 600 mg oral gabapentin administered pre-operatively at the time of cervical preparation initiation will improve intra-operative pain control. We also hypothesize that it will improve pre- and post-operative pain, anxiety, nausea, vomiting, and overall satisfaction with pain management during D&E. We hypothesize that the doses of moderate sedation agents required to obtain adequate sedation will be decreased in patients receiving gabapentin versus placebo. We also plan to compare the risk of adverse events with adjunct gabapentin versus placebo with moderate sedation.

To test our hypotheses we plan to enroll 130 participants who will be randomized 1:1 to receive either 600 mg gabapentin or placebo at the initiation of cervical preparation. Baseline participant characteristics will be recorded. Pain will be assessed pre-operatively, at 3 intraoperative time points, and postoperatively by 100 mm visual analog scale (VAS). We plan to assess satisfaction with pain control, nausea, vomiting, and anxiety preoperatively and post-operatively, using 5-point Likert scales and the State Trait Anxiety Inventory, respectively. A final assessment will be made by phone on post-operative day one to evaluate overall satisfaction and perform a final screen for adverse events.

New features.

No publications have evaluated the use of gabapentin during abortion care, although multiple studies are currently underway investigating gabapentin's effects during first trimester abortion and during overnight cervical osmotic dilators. To our knowledge, this will be the first evaluation of gabapentin in conjunction with moderate sedation for pain relief during same-day second trimester abortion.

Problems anticipated.

Gabapentin does have a sedating effect and, when used in conjunction with moderate sedation and oral opioids, may lead to increased sedation. We have chosen a relatively low dose of gabapentin to minimize this potential risk. We also plan to limit daily recruitment to minimize disrupting clinic flow and ensure that the study coordinator is available to conduct all assessments on all participants.

1. DESCRIPTION OF THE PROJECT

1.1 Rationale and objectives of the study

1.1.1 Rationale

Over 900,000 induced abortions are performed in the United States annually and 8.6% are dilation and evacuation (D&E) over 13 weeks gestation [1][2]. As over half of abortions are surgical

in nature, the Society of Family Planning has identified “pain management preferences for abortion” as a research priority [3]. The vast majority of the research on pain management during abortion has been conducted in the first trimester. Safe and efficacious options for pain management during abortion include local anesthetics, NSAIDs, anxiolytics, opioids, sedatives, hypnotics, and general anesthesia. Most studies evaluating paracervical block, NSAIDs, oral sedation, and IV sedation demonstrate efficacy in pain reduction [4]. Despite reduction in pain with NSAIDs, paracervical block, and IV sedation, many women still experience inadequate pain relief at the time of surgical abortion.

Gabapentin (Neurontin®), has recently emerged as an effective adjunct to pain management for a variety of surgical procedures but has yet to be studied for perioperative pain control during second-trimester abortion. Gabapentin is a gamma-amino butyric acid (GABA) analog and is approved by the U.S. Food and Drug Administration (FDA) for treatment of post-herpetic pain and seizure disorders. Off-label uses include the treatment of neurologic, chronic and surgical pain. The primary mechanism of action is believed to be modulation of voltage-gated calcium channels and inhibition of release of neurotransmitters [5].

Gabapentin is successfully being used as an adjunct to pain control during both inpatient and outpatient surgical procedures, such as hysterectomy, orthopedic, and ear-nose-throat (ENT) procedures. It is relatively inexpensive. The addition of pre-operative gabapentin to moderate sedation during D&E may lead to increased patient satisfaction and pain control without significantly increasing risk or cost. It may also reduce anxiety, nausea, and vomiting and allow providers to use lower doses of sedatives, improving anesthetic safety.

1.1.2 Objectives and hypotheses

Objective 1: To compare the effect of gabapentin 600 mg to placebo on intraoperative pain during D&E under moderate sedation.

We hypothesize that administration of gabapentin will lower reported pain during D&E compared to placebo.

Objective 2. To compare the effect of gabapentin 600 mg to placebo on the total dose of IV sedation (fentanyl and midazolam) during D&E.

We hypothesize that administration of gabapentin will reduce the total dose of IV sedation agents compared to placebo.

Objective 3. To compare the effect of gabapentin 600 mg to placebo on pre- and post-operative pain, anxiety, nausea, vomiting, and overall satisfaction with pain management.

We hypothesize that administration of gabapentin will result in lower pre- and post-operative pain, anxiety, nausea, and vomiting, and higher satisfaction with pain management compared to placebo.

Objective 4. To compare the adverse events and risks of gabapentin to placebo.

We hypothesize that pre-operative administration of gabapentin will not increase adverse events compared to placebo.

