1.3 Design and methodology

1.3.1 Research design and General Methodological Approach

We propose a randomized controlled double-blinded trial comparing oral gabapentin 600 mg to placebo among patients undergoing outpatient same-day dilation and evacuation under moderate sedation. We propose to give the study drug (gabapentin or placebo) shortly after the initiation of same-day cervical preparation and a minimum of one hour prior to D&E. The primary study outcome is maximum pain during D&E as recorded by 100-mm VAS (Table 1). Secondary outcomes include total doses of IV sedation, pain at three time points during D&E, perioperative pain, anxiety, nausea, vomiting, patient satisfaction with pain management, oxygen saturation during moderate sedation, and administration of sedation reversal agents. We will also contact patients by phone on post-operative day 1 (POD1) to assess for prolonged or delayed side effects, adverse events and overall satisfaction with pain control.

Study medications will be administered by study staff, Planned Parenthood of Metropolitan Washington DC (PPMW) staff, or MedStar Washington Hospital Center (MWHC) staff after initiation of cervical preparation. The MedStar Health Research Institute (MHRI) pharmacy will prepare identical capsules containing gabapentin 600 mg or methylcellulose placebo. The pharmacy will package the capsules in sequentially numbered opaque sealed envelopes according to a computer-generated 1:1 randomization scheme prepared by MHRI. Study staff involved in administering medications and assessing outcomes, clinical staff (health care associates, nurses, physicians), and participants will be blinded to randomization assignment. Randomization assignment will only be revealed at the time of data analysis or in the case of a serious adverse event. As there is no standard or optimal dose of pre-operative gabapentin, we have chosen to use a dose of 600 mg with the aim of maximizing pain relief while minimizing the sedative effect. This is the same dose currently being investigated during first-trimester abortion at Emory University.

Administration of analgesics, anesthetics, and anti-emetics will be standardized. Patients will generally receive the following oral pre-procedure regimen: naproxen 500 mg, ~~tramadol 50 mg,~~

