alprazolam 0.25 mg, promethazine 25 mg, and azithromycin 500 mg. Medications may be adjusted per provider judgement and patient characteristics, such as allergies. At the time of D&E, providers will administer a paracervical block using 20 mL of 1% lidocaine with 4 units vasopressin. Initial doses of moderate sedation at both sites will be 1 mg midazolam and 50 mcg fentanyl. Additional doses are sometimes required intraoperatively to achieve adequate pain relief and will be left to provider discretion. Total doses of moderate sedation will be capped at 5 mg midazolam and 200 mcg fentanyl. Total doses of midazolam and fentanyl will be documented.

Assessments and tools:

Pain will be assessed using 100-mm VAS. We will assess pre-operative pain using VAS while the patient awaits moderate sedation administration in the procedure room. We will assess intra-operative pain at the following time points: within one minute after speculum placement, within one minute after the initiation of uterine suction aspiration, and within one minute after speculum removal. An assessment of “maximum” intra-operative pain will be made 3- 5 minutes after speculum removal. VAS will be used to assess post-operative pain 30 minutes (range 20-40 minutes) after the procedure. Assessments of anxiety will be made using 20-items of state anxiety from the State Trait Anxiety Inventory (STAI), a validated tool for measurement of anxiety that is used frequently in abortion research [19], [20]. Anxiety will be assessed prior to administration of moderate sedation and 30 minutes post-procedure. Nausea, vomiting, and satisfaction with pain control will be assessed using 5-point Likert scale prior to the administration of moderate sedation and 30 minutes post-procedure. Lowest intra-operative oxygen saturation as measured via pulse oximeter and administration of reversal agents will be recorded. Adverse events will be monitored and include, but are not limited to, seizure-like activity, need for sedation reversal agent, respiratory depression (oxygen saturation <90%), use of uterotonics, aspiration of emesis, or transfer to hospital. Overall satisfaction with pain control will also be assessed on POD1 using a 5-point Likert scale. Participants will receive financial compensation in the form of a \$40 gift card on the day of the procedure for their time and participation. After completion of the phone assessment on POD1, participants will be mailed a \$10 gift card.

Table 1: Assessments

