1.3.10 Data analysis

Data analysis will be conducted using Stata. The baseline characteristics of the populations will be described. Intention-to-treat analysis will be performed. Primary continuous outcome (pain score on 100-mm point VAS) for the two treatment groups will be compared using T-tests, and if appropriate, by non-parametric analysis. Secondary outcomes will be compared using Chi-square and T-tests, as applicable. Baseline characteristics will be evaluated for potential interaction or confounding with primary and secondary outcomes. If we observe 5 serious adverse events (SAE) requiring sedation reversal agents before enrolling 50 participants, we will ask the statisticians to unblind allocation and

perform an interval analysis to assess for a relationship between study arm and risk of SAE. Once 50 participants are enrolled, we will ask the same analysis after 6 events occur. These numbers of events are based on the concept that if all of the events are in one treatment arm we would find a statistically significant difference in SAE risk between the arms. For reference, sedation reversal is used in less than 1% of D&Es at both sites. Participants may request that their data not be used for analysis if a request is received prior to analysis as mentioned in the consent form. MedStar Health Research Institute (MHRI) statisticians will be consulted to assist with the analysis as needed.

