1.3.12 Study limitations

We are aware that the standard regimen for moderate sedation during second trimester abortion at our facilities (naproxen, tramadol, alprazolam, fentanyl, and midazolam) may provide greater pain relief and sedation than other commonly used regimens and thus may limit our ability to detect an improvement in pain relief. However, our experience is that a significant proportion of women have inadequate pain control despite receiving the standard regimen and therefore they may benefit from gabapentin. The fact that gabapentin has been shown to reduce total narcotic use after major surgery is reassuring. Our sample size limits our ability to detect rare outcomes or complications such as medication adverse reactions.

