1.6 Main problems anticipated

The frequency of intraoperative pain assessments will require the study coordinator to remain in the room throughout the procedure and therefore we will limit recruitment to 4 patients per day per site to minimize disruptions to clinic flow. This will also reduce the chance of missing data from

perioperative assessments as a result of the coordinator's unavailability. We also anticipate some loss to follow up at the time of the POD1 assessment; this assessment is a secondary outcome and we are taking steps to minimize loss as described in section 1.3.6. Our final concern relates to the potential for over-sedation with the combination of gabapentin and opioids, which could impact both patient safety and clinic flow if discharge is delayed. Although dose-finding studies have not identified an ideal dose, we suspect that a one-time dose of 600 mg will improve pain control without significantly contributing to sedation. Sedation reversal agents are available at both sites. Adverse events, including respiratory depression, will be monitored, reviewed, and allocation revealed if necessary.

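### Objective 4 expects no increase in adverse events, but the only final method that reaches them is a difference test without a confidence interval, which cannot support that claim at about 65 per arm

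*Combined protocol and SAP*

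**What the plan says.** Safety is one of four numbered objectives. Objective 4 in section 1.1.2 sets out to compare adverse events and risks between the arms, and adds a directional expectation: "We hypothesize that pre-operative administration of gabapentin will not increase adverse events compared to placebo". The Project Summary makes the same commitment: "We also plan to compare the risk of adverse events with adjunct gabapentin versus placebo with moderate sedation".

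Section 1.3.1 names two safety measures among the secondary outcomes: "oxygen saturation during moderate sedation, and administration of sedation reversal agents". It introduces that list as what the secondary outcomes include, so the list need not be complete. It also gives examples of the adverse events to be monitored, among them need for a reversal agent and saturation below 90%, and says that adverse events will be assessed by telephone on post-operative day 1.

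For the final analysis, section 1.3.10 says: "Secondary outcomes will be compared using Chi-square and T-tests, as applicable". It does not name adverse events there and mentions no confidence interval or margin. Its one analysis specific to adverse events is a conditional unblinded look after five or six serious events requiring reversal. For context it says that "sedation reversal is used in less than 1% of D&Es at both sites".

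Section 1.3.12 concedes: "Our sample size limits our ability to detect rare outcomes or complications such as medication adverse reactions".

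**The concern.** A chi-square test asks whether the data are inconsistent with equal risks. When it is not significant, the data are compatible with equality, but also with every other difference inside the confidence interval. At this sample size that interval includes excesses large enough to matter. A hypothesis of no increase paired with a difference test therefore has its logic reversed: the less information the trial collects, the more easily the hypothesis appears to be confirmed.

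The misreading is foreseeable. Section 1.2 reports that a large meta-analysis found no significant association between gabapentin and respiratory depression; section 1.3.4 restates the same source as having shown no increase. Section 1.7 expects the trial to add to knowledge of gabapentin's safety alongside moderate sedation, possibly for other specialties. A safety sentence resting on a non-significant test would travel without any statement of the excess risk that the data still allow.

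**Working it through.** **Inputs from the documents.** 130 participants randomised 1:1, so 130 / 2 = 65 per arm (sections 1.3.1 and 1.3.11); 59 per arm before the allowance for incomplete data; alpha 0.05. The only background event rate given is below 1%, for sedation reversal. No adverse-event rate for planning and no margin is stated, so the rates used for power below are assumptions.

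**The plan's own figure.** For the pain outcome, n per arm = 2 × (SD / difference)² × (1.960 + 0.842)² = 2 × (25 / 13)² × 7.849 = 58.05, rounded up to 59. This reproduces the stated figure as a two-sided test (a one-sided test would give 46). The trial is sized for pain; no size or power is stated for adverse events.

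**Which method reaches adverse events.** The Project Summary plans the comparison, the list in section 1.3.1 is open-ended, and section 1.3.10 gives chi-square for categorical secondary outcomes. It is reasonable to infer that adverse events fall under that sentence. The check below takes this as the planned analysis.

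**Intervals for possible results (no event rate assumed).** The Newcombe interval combines the Wilson limits (l, u) of each arm, with arm 1 gabapentin, arm 2 placebo and d = p1 - p2:

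- lower = d - √[(p1 - l1)² + (u2 - p2)²]
- upper = d + √[(u1 - p1)² + (p2 - l2)²]

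*0 vs 0 of 65.* The Wilson upper limit is z² / (n + z²) = 3.841 / 68.841 = 0.0558. The interval is -5.6 to +5.6 points.

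*3 vs 0 of 65.* p1 = 0.0462, with Wilson limits 0.0158 and 0.1271.

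- Lower = 0.0462 - √(0.0303² + 0.0558²) = -0.017
- Upper = 0.0462 + 0.0810 = 0.127
- Chi-square = 130 × (3 × 65)² / (65 × 65 × 3 × 127) = 3.07, p = 0.080; Fisher p = 0.244

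This result is non-significant, with an interval of -1.7 to 12.7 points.

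*6 vs 6 of 65.* p = 0.0923 in each arm, with Wilson limits 0.0430 and 0.1871. Upper = √(0.0948² + 0.0493²) = 0.107, or 10.7 points.

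With 59 per arm the same three results give upper limits of 6.1, 13.9 and 11.6 points.

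**Power of the planned test (rates assumed).** Power is the sum, over all pairs of counts, of the product of the two binomial probabilities wherever the two-sided p-value is below 0.05. Chi-square is uncorrected.

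| Placebo vs gabapentin | 65 per arm: chi-square / Fisher | 59 per arm: chi-square / Fisher |
|---|---|---|
| 1% vs 5% (rare, reversal-type) | 23% / 6% | 20% / 4% |
| 5% vs 10% | 19% / 10% | 17% / 9% |
| 10% vs 20% (commoner) | 35% / 28% | 34% / 24% |

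With 65 per arm, chi-square would miss a rise from 1% to 5% 77% of the time (100 - 23) and a doubling from 10% to 20% 65% of the time (100 - 35). The weakness is not confined to rare events.

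**The case against.** The strongest reply is that the harm has not happened and may not. Objective 4 itself is neutral, to compare; only the hypothesis sentence speaks of no increase, and that is an expectation, not a decision rule. A reader might infer that the sponsor intends to declare gabapentin safe if the test is not significant. The documents do not say so, and section 1.3.12 points the other way. That stands, and it limits the point to a mismatch between claim and method. But section 1.3.12 speaks of rare outcomes only and leaves both the hypothesis and the analysis as they are.

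A reader might also infer that adverse events have no final analysis at all. That goes too far: the Project Summary, the open-ended list in section 1.3.1 and the general sentence in section 1.3.10 together cover them well enough. They are not named there, which is different from being absent.

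It can also be said that section 1.3.10 plans no interval for any outcome, and that silence in a short analysis section does not mean none will be reported. True, but Objective 4 is where the omission decides whether the stated hypothesis can be addressed.

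The monitoring provisions in sections 1.3.7 and 1.3.10 are sometimes offered as an answer. They protect participants during the trial. The five- or six-event look is conditional, limited to reversal events, and is itself a difference test; it supplies no final inference.

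Finally, section 1.6 worries about over-sedation, "which could impact both patient safety and clinic flow if discharge is delayed", and a reader might infer that time to discharge must become a safety outcome. That is a matter of preference, does not bear on the inferential gap, and forms no part of this point.

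**Conclusion.** The point holds in this form: the hypothesis of no increase cannot be supported by the only final method the plan offers. With 65 per arm, even an event-free trial leaves an excess of 5.6 points open, and equal counts of six leave 10.7 points. These limits assume complete data, 65 per arm and the Newcombe method, but no event rate. The power figures of 23% and 35% rest on assumed rates; the first describes only rare, reversal-type events, a weakness that section 1.3.12 already partly discloses. The primary pain comparison is unaffected. The plan should be changed because a numbered objective cannot be answered as written, not because the trial is too small for a secondary safety objective or because a false safety claim has been announced.

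**What to change.** - Restate Objective 4 as estimation of the difference in adverse-event risk between the arms, and drop the hypothesis of no increase.
- In section 1.3.10, name the endpoints: participants with any adverse event, with reversal agent use, and with saturation below 90%.
- For each, report counts and the risk difference with a 95% confidence interval by a method valid at zero counts (for example Newcombe) as the main result, in place of the chi-square test.
- State that a non-significant difference will not be reported as showing no increase, and word the conclusion as the largest excess the data do not exclude.

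This needs no margin, extra participants or new data; the cost is wording. It does not raise power. The real downside is a less favourable and often inconclusive safety statement. With 65 per arm and no true difference, the median upper limit would be 5.6 points at an assumed 1% event rate (10th to 90th percentile 4.2 to 9.1) and 8.6 points at an assumed 5% rate (3.0 to 14.0).

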1.2 Previous similar studies

A number of well-designed studies have evaluated pain management during first-trimester abortion. A combination of paracervical block and IV sedation is more effective than paracervical block alone, with the combination resulting in a mean pain score of 43-46 mm (SD 23-26) on a 100-mm visual analog scale (VAS) during first-trimester abortion [6]. In a prospective randomized controlled trial (RCT) of IV sedation (midazolam 2 mg and fentanyl 100 mcg) compared to oral sedation for first-trimester abortion, patients receiving IV sedation had significantly lower pain scores with a mean score of 36.3 (SD 26.5) vs. 61.2 (SD 25.2) on a 100-point scale [7]. Other RCTs evaluating IV sedation used lower doses of IV agents, with and without paracervical block, and found higher mean pain scores, with confidence intervals ranging from 3.7 to 5.5 on a 10-point scale [8], [9]. We could find no published studies dedicated to pain control during second-trimester abortion.

Within the last decade many studies have evaluated the use of gabapentin in prevention and treatment of peri-operative pain. The largest meta-analysis on prophylactic gabapentin was published in 2015 [10]. Of the 133 included studies, over 20 involved gynecologic procedures. Pre-operative doses of gabapentin ranged from 100 mg to 1200 mg. They found that pre-operative gabapentin was associated with reduced anxiety, pain scores, and opioid use in the first 24 hours after surgery. It was also associated with reduced nausea, vomiting, and pruritus and increased patient satisfaction and sedation. Despite increased sedation with gabapentin use, there was no significant association between respiratory depression and gabapentin use. Six randomized controlled trials have examined the relationship between pre-operative gabapentin and respiratory depression and none found an association [11]–[16]. An earlier meta-analysis of gabapentin prior to abdominal hysterectomy included 14 trials and concluded that pre-operative gabapentin reduced post-operative morphine consumption, pain, and nausea [17].

Evaluation of the effect of gabapentin on intraoperative outcomes and in combination with sedation is limited. A single study investigating pre-operative gabapentin during deep sedation for ENT surgery found decreased consumption of intraoperative sedation agents (fentanyl), decreased use

of rescue analgesic, and reduced intraoperative pain scores [18]. They did note increased dizziness in the gabapentin group. Gabapentin has also been found to improve pain scores and decrease consumption of fentanyl when used for pain control during intensive care unit admission [15]. Dose-finding studies have been limited by inadequate sample size, but their findings suggest that pre-operative doses of at least 600 mg to 900 mg provide post-operative benefit [5].

